13 OUTCOME MEASURES

13.1 PRIMARY OUTCOME MEASURE

The primary outcome measure of the LaCeS2 trial is the incidence of 30 day post-operative complications. This is defined as the number of patients with a post-operative complication (of any grade) occurring within 30 days of surgery as a proportion of all randomised patients.

13.2 KEY SECONDARY OUTCOME MEASURES

- Patient reported outcomes and Quality of Life Outcomes
 All patient reported outcomes are collected during the 30 days, 3, 6, 9 & 12 months post-surgery.
- a) 12-Item Short Form Survey (SF-12)

This patient reported outcome consists of 12 items, covering 8 health domains (Physical Function, Role-physical, Bodily Pain, General Health, Vitality, Social Functioning, Role-emotional & Mental Health), combined into physical & mental component scores (PCS & MCS).

b) Gastrointestinal Quality of Life Index (GIQLI)

The Gastrointestinal Quality of Life Index (GIQLI) questionnaire will be used to measure gastrointestinal related HRQoL [13] over the 12 month follow-up period. This questionnaire consists of 36 items, each scored between 0 - 4 points, to be summed up for a total aggregate score on the continuous scale 0 - 144, with 144 representing

best HRQoL [23]. In addition to the total score, there are also 5 subscales (GI symptoms, Emotion, Physical Function, Social Function & Medical Treatment), which can be summed to produce subscale scores [24].

13.3 SECONDARY OUTCOME MEASURES

2) 30-day post-operative complications severity

a) Clavien-Dindo (CD) Classification

All post-operative complications will be graded according to the Clavien-Dindo (CD) Classification [20, 25]. This is an acceptable and validated method of documenting surgical complications. The CD Classification system assigns a grade to the most severe complication experienced. The system is divided into 7 grades (I, II, IIIa, IIIb, IVa, IVb and V), reflecting the varying severity of complications (Table 1, Appendix B).

b) Comprehensive Complication Index (CCI)

The Comprehensive Complication Index [22] is used as a validated method to measure all complications experienced, measuring the overall magnitude of all complications experienced [26]. The CCI is calculated as the sum of all complications weighted by severity, measured using the CD classification for post-operative complications. The CCI is a continuous scale which ranks the severity of any combination of complications from 0 (no complications) to 100 (death) in a single patient.

3) 90-day post-operative and surgery specific complications

a) 90-day post-operative complications

The incidence of 90-day complications is defined as the number of patients with a complication occurring within 90 days post-operatively as a proportion of all randomised patients.

b) Surgery-specific complications

The incidence of surgery-specific complications is calculated as the number of patients experiencing a surgery-specific complication within 6 & 12 months as a proportion of all randomised patients. Examples of surgery-specific complications are listed in Appendix 2, although the list is not exhaustive.

4) Intra-operative complications and intra-operative conversions from laparoscopic to open surgery

a) Intra-operative complications

The incidence of intra-operative complications is defined as the number of patients with intra-operative complications recorded as a proportion of all randomised patients. Intra-operative complications will be graded according to the ClassIntra® v1.0 classification of intra-operative adverse events (see Appendix 4).

b) Intra-operative conversions from laparoscopic to open surgery

An intra-operative conversion from laparoscopic to open surgery is defined as the use of a midline laparotomy wound for any part of the colorectal dissection during the procedure. The incidence of conversions from laparoscopic to open surgery is calculated as the number of patients experiencing a conversion as a proportion of all patients allocated to receive laparoscopic surgery.

5) Post-operative patient mortality, re-operations and readmissions

a) **30-day post-operative mortality**

Mortality rates are defined as the number of patients that have been recorded as dead within the 30 days following surgery as a proportion of all randomised patients.

b) 30-day post-operative re-operations

The incidence of re-operations is defined as the number of patients that have recorded an additional abdominal surgical procedure within the 30 days following surgery as a proportion of all randomised patients.

c) 30-day post-operative readmissions

The incidence of 30 day post-operative readmissions is defined as the number of patients that have recorded a readmission to hospital following initial discharge within the 30 days following surgery as a proportion of all randomised patients.

6) Restoration of gastrointestinal function

a) Time to gastrointestinal function resumed

Gastrointestinal function is defined as dietary intake (i.e. Consumption of food) AND bowel function (passage of stool) in keeping with the GI-2 definition [27]. Therefore, the time to restoration of gastrointestinal function is calculated as the time, in days, from surgery to dietary intake AND bowel function resumed.

- 7) Length of hospital stay
- a) Time to discharge

Length of hospital stay is calculated as the time, in days, from surgery to patient declared medically fit for discharge.

- 8) Cost-effectiveness
- EQ-5D-5L (30 days, 90 days, 6 months, 9 months and 12 months post-operation)
- Health resource utilisation assessed at 30 days, 90 days, 6 months, 9 months and 12 months post-operatively
- 9) Qualitative study
- An understanding of the recruitment barriers from the perspective of patients to inform staff/recruiter training.
- An understanding of the trial from the perspective of staff/recruiters at sites.

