9.4.3 TREATMENT ALLOCATION

Participants will be randomised on a 1:1 basis to receive either laparoscopic or open surgery and will be allocated a unique trial number. Randomisation will be based on a minimisation algorithm with random component ensuring that treatment groups will be balanced for the following minimisation factors:

- Intended Consultant Surgeon in charge
- Patient age
 - o **18-<50**
 - o **50-59**
 - o **60-69**
 - o **70-79**
 - o ≥80
- Body Mass Index (kg/m²)
 - <25 kg/m²
 - o 25-<30 kg/m²
 - o ≥30 kg/m²
- ASA status
 - o I or II A normal healthy patient or A patient with mild systemic disease.
 - III A patient with severe systemic disease.
 - IV Or V A patient with severe systemic disease that is a constant threat to life or A moribund patient who is not expected to survive without the operation.
- Nature of underlying colorectal pathology
 - o Benign
 - o Malignant
 - o Unsure
- Nature of intended surgical procedure
 - Segmental colectomy, Right hemicolectomy, Left Hemicolectomy or Sigmoid Colectomy
 - Hartmann's procedure
 - o Subtotal colectomy
 - o Other

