11.4 FOLLOW-UP DATA COLLECTION

11.4.1 DISCHARGE DETAILS

Hospital discharge details will be entered onto the Discharge eCRF in the LaCeS2 database at the point at which participants are discharged from hospital. Data collected will include (but will not be limited to):

- Date of discharge
- Date of restoration of gastrointestinal function, if applicable

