11.4.3 DATA COLLECTION FOR CLINICAL ASSESSMENTS

Post-operative care will be as per institutional protocol. However, a clinical assessment must be carried out for all participants at 6 weeks and 90 days post-operation. The 6-month and 12-month post-operative assessment can be completed from participants' medical notes; participants do not need to be seen in clinic for trial purposes at these time points. Data collected during follow-up will include (but will not be limited to):

- Participant status (dead/alive)
- Complications
- Readmissions
- Reoperations (see section 11.4.2 for additional details)
- Details of further abdominal surgeries

At the post-operative reviews participants will be asked to complete the participant questionnaire booklets; for details of questionnaires completed at each post-operative review refer to section 11.5.

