14.4 ANALYSES OF SECONDARY OUTCOME MEASURES

Secondary outcomes will be analysed according to the nature of the corresponding measures. Binary measures which include:

- Incidence of 90-day complications
- Surgery-specific complications within 6 & 12 months post-operatively
- Intra-operative complications

30-day post-operative mortality, re-operations and readmissions will be analysed differently from continuous measures which include:

- Patient-reported Quality of Life measures (SF-12 & GIQLI)
- Severity of 30-day post-operative complications, using CCI
- Time to restoration of gastrointestinal function
- Length of stay

Binary secondary outcome measures will be analysed using multi-level logistic regression models, adjusted for all minimisation factors whilst incorporating random effects with respect to treating surgeon. Adjusted treatment effects will be reported alongside 95% confidence limits.

Continuous secondary outcome measures will be analysed using multi-level linear models, adjusted for all minimisation factors whilst incorporating random effects with respect to treating surgeon. Models for the patient reported outcomes (SF-12 & GIQLI) will include an additional level to account for repeated measures due to the longitudinal nature of the data.

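### Time to gut recovery: the only named source of the date is the discharge form and the model is linear, so patients who leave or die before recovery cannot be used as observed, and stoma output is undefined

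*Protocol*

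**What the plan says.** The outcome has two components that must both occur. Section 13.3, item 6a: "Gastrointestinal function is defined as dietary intake (i.e. Consumption of food) AND bowel function (passage of stool) in keeping with the GI-2 definition". The same item adds that "the time to restoration of gastrointestinal function is calculated as the time, in days, from surgery to dietary intake AND bowel function resumed". No end of observation is given, and no value for a patient in whom one component has not occurred.

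The date is placed on the Discharge eCRF, completed "at the point at which participants are discharged from hospital", in the field "Date of restoration of gastrointestinal function, if applicable" (section 11.4.1). The follow-up list in section 11.4.3 does not name it, and Table 1 has no row for it. That list is open, however: "Data collected during follow-up will include (but will not be limited to").

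Section 14.4 separates the binary outcomes, which "will be analysed differently from continuous measures which include" this one by name. It then states: "Continuous secondary outcome measures will be analysed using multi-level linear models". Section 14.5 allows imputation and leaves its details to the SAP.

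Stomas are expected. "Hartmann's procedure" is a minimisation category in section 9.4.3, and stoma necrosis is among the expected complications in Appendix 2. The definition in 13.3 does not mention stomas.

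**The concern.** Two separate matters are at stake.

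**Capture and model.** Observation of this endpoint appears to stop at discharge, an event that treatment may itself affect: length of stay is another outcome of the trial, and the trial is unblinded. A patient who goes home eating but before passing stool has a recovery time known only to exceed the stay. A patient who dies before recovery never has one. A linear model needs a number for each patient, so the first kind must be dropped or given an invented value, and for the second no value exists. If the share lost differs by arm, slow recoveries are removed unequally.

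**Definition.** Without a sentence on stoma output, one site may enter the date of first output while another leaves the field empty. With at least 25 sites, that makes the data inconsistent and incomplete.

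**Working it through.** **Plan's own figure.** There is none. The protocol gives no recovery time, no discharge time by arm, no share discharged before recovery and no stoma rate. Every input below is an assumption, used only to show when the problem matters.

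**Step 1: the provisions together.** Definition: both events are needed (13.3). Named capture: at discharge, where applicable (11.4.1). Later capture: none named (11.4.3, Table 1). Model: linear (14.4). The words qualifying the discharge field already accept that some patients will have no date.

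**Step 2: share without a date.** Let recovery be G = 4.5 × exp(0.6·Z1), identical in both arms, and discharge be D = m × exp(0.6·(ρ·Z1 + √(1−ρ²)·Z2)), where m is the median discharge day, ρ the correlation on the log scale, and Z1 and Z2 independent standard normals. The true mean is 4.5 × exp(0.18) = 5.39 days. Then

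Pr(no date) = Φ(−ln(m/4.5)/v), with v = √(0.36 + 0.36 − 2ρ·0.36).

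At ρ = 0.5, v = 0.6:
- m = 10: Φ(−0.799/0.6) = 9.2%
- m = 8: Φ(−0.575/0.6) = 16.9%
- m = 7: Φ(−0.442/0.6) = 23.1%

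**Step 3: spurious difference if undated patients are dropped.** Simulated means among patients with a date (2,000,000 draws per arm), with the true difference equal to zero:

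| ρ | m = 10 | m = 8 | m = 7 | 10 v 8 | 10 v 7 |
|---|---|---|---|---|---|
| 0.5 | 5.030 | 4.830 | 4.683 | 0.20 d | 0.35 d |
| 0.8 | 5.330 | 5.230 | 5.125 | 0.10 d | 0.20 d |
| 0.9 | 5.388 | 5.354 | 5.302 | 0.03 d | 0.09 d |

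At ρ = 0.5, 10 v 8, the SDs are 3.13 and 2.96, and 256 × 0.908 = 232 and 256 × 0.831 = 213 patients have dates. The SE is √(3.13²/232 + 2.96²/213) = 0.29, so 0.20 days is about 0.7 SE.

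**Step 4: a second set of assumptions.** Recovery median 4 days with log-SD 0.5 to 0.7, discharge log-SD 0.5, correlation 0 to 0.6:
- Discharge 6 v 8 days: 18–32% v 6–21% undated. The spurious difference is 0.2 to 0.5 days if they are dropped and 0.2 to 0.4 days if the discharge date is substituted.
- Discharge 7 v 7 days: about 0.
- Discharge 5 v 9 days, a much wider gap: 0.4 to 1.0 days.

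**Step 5: would censoring at discharge be enough?** No. With discharge correlated with recovery, the censoring is informative. At ρ = 0.5, the Kaplan–Meier restricted mean to 21 days is 5.50 (m = 10) against 5.63 (m = 8) or 5.74 (m = 7), when the true value is 5.36 in every case. The bias changes sign: the arm discharged earlier now looks slower, by 0.13 or 0.24 days.

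**Step 6: stoma.** No arithmetic applies, because the protocol gives no stoma rate. Intended procedure is a minimisation factor and a model covariate, so the ambiguity would tilt the comparison only if stoma rates or recording habits differed by arm.

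**The case against.** The best defence is that this is SAP territory. Section 14.5 defers missing-data methods, section 14.1 says analyses will be predefined in the SAP, and section 16.2 has missing data chased. The data lists are open-ended and the forms are not shown, so a later date may be sought. The stool definition does not specify a route, and the gastrointestinal-motility study it cites may settle the stoma question.

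Much of this stands. The absence of a scoring rule is not in itself an error, and the protocol does not say that undated patients will be dropped. But the model is not left open: 14.4 fixes it. A SAP cannot recover a date that no form requested, or settle afterwards how sites read the stool criterion. Imputation would have to learn from patients who recovered before discharge in order to fill in patients known to have recovered after it, and it has nothing to offer for deaths.

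A reader might infer three stronger things that the documents do not support:
- **That the date is recorded only at discharge.** Discharge is the only place named, and the lists are not exhaustive.
- **That the result will favour laparoscopy.** This needs earlier discharge in that arm, a real share leaving before recovery, and those patients being dropped or given the discharge date. The protocol shows none of these. Section 5.1 cites reviews reporting shorter stay but calls their methods weak.
- **That the stoma gap biases the comparison or removes a large part of the population.** No stoma rate is given, and the gap has no inherent direction.

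**Conclusion.** The point holds as a mismatch between endpoint, named capture and model. A two-component time outcome, with discharge as the only named source of its date, is committed to a model that cannot represent patients who leave or die before the event. The direction of any bias is conditional, and its size is illustrative only: about 0 to 0.5 days under assumed two- to three-day gaps in median discharge, larger only if the gap is wider, and near zero if stays are equal or few patients leave before recovery. The stoma omission is a real but directionless gap in definition. This is a secondary outcome that section 14.6 says is not powered, and the primary result is untouched. A change is still worth making because it is cheap and the missing dates cannot be reconstructed later.

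**What to change.** - **13.3, item 6a:** state whether stoma output counts as bowel function.
- **11.4.1:** replace the single conditional date with separate dates for food intake and for stool, each with a *not yet at discharge* option. Complete any outstanding date on the existing 6-week follow-up form, as the main route to full data.
- **14.4:** take this outcome out of the linear-model group and specify a time-to-event method that treats death before recovery as a competing event, keeping the surgeon effect and the minimisation factors. Do not rely on censoring at discharge, which step 5 shows to be informative.

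The cost is one sentence of definition, small changes to two forms and one line of 14.4. The drawback is that dates after discharge rest on patient recall at about 6 weeks.

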14 STATISTICAL CONSIDERATIONS

14.1 GENERAL CONSIDERATIONS

Statistical analysis is the responsibility of the CTRU Statistician (apart from the Health Economics analysis, details of which can be found in section 15). A full approved, version-controlled statistical analysis plan (SAP) will be written before any analyses are undertaken, according to guidelines published [28]. All analyses and patient populations will be predefined within the trial's SAP and reporting will be in line with CONSORT guidelines [29, 30]. As LaCeS2 is a superiority trial, the primary analysis will be based on an intention to treat (ITT) patient population, where all patients are analysed according to their randomised allocated treatment.

14.2 FREQUENCY OF ANALYSES

For the purposes of monitoring patient safety outcomes and data quality, interim reports will be completed on an annual basis for presentation to the DMEC. The DMEC will also monitor underlying assumptions of the statistical design, particularly the underlying assumptions of the control arm. Analyses will be agreed and documented upfront by the independent DMEC members. The DMEC, in the light of the interim data, and of any advice or evidence they wish to request, will advise the Trial Steering Committee if there is justification to consider closing the trial. No formal guidelines for stopping the trial early are in place since no formal interim analysis of the primary outcome measure is planned.

14.3 PRIMARY OUTCOME MEASURE ANALYSIS

The primary analysis of LaCeS2 will compare the primary outcome measure of the incidence of 30-day post-operative complications between patients randomised to undergo laparoscopic or open surgery. An adjusted treatment effect will be estimated using a multi-level logistic regression model, incorporating a random effect with respect to treating surgeon and adjusting for all minimisation factors listed above (Section 9.4). Statistical significance of the treatment effect within the statistical models will be based upon a 2-sided 5% level. This approach will be used to test a two-sided hypothesis that the complication rate is equal in both arms, suggesting an odds ratio equal to 1. Opposed to an alternative superiority hypothesis that the incidence of complications is 15% lower within those allocated to the laparoscopic surgery compared to those allocated to the open surgery group. A secondary analysis of the primary outcome measure will be performed where patients are analysed according to the actual surgery received (open, laparoscopic or laparoscopic converted to open surgery).

14.4 ANALYSES OF SECONDARY OUTCOME MEASURES

Secondary outcomes will be analysed according to the nature of the corresponding measures. Binary measures which include:

- Incidence of 90-day complications
- Surgery-specific complications within 6 & 12 months post-operatively
- Intra-operative complications

30-day post-operative mortality, re-operations and readmissions will be analysed differently from continuous measures which include:

- Patient-reported Quality of Life measures (SF-12 & GIQLI)
- Severity of 30-day post-operative complications, using CCI
- Time to restoration of gastrointestinal function
- Length of stay

Binary secondary outcome measures will be analysed using multi-level logistic regression models, adjusted for all minimisation factors whilst incorporating random effects with respect to treating surgeon. Adjusted treatment effects will be reported alongside 95% confidence limits.

Continuous secondary outcome measures will be analysed using multi-level linear models, adjusted for all minimisation factors whilst incorporating random effects with respect to treating surgeon. Models for the patient reported outcomes (SF-12 & GIQLI) will include an additional level to account for repeated measures due to the longitudinal nature of the data.

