Acceptability and Feasibility: Baseline compliance for clinical data was 99.8% and for health related quality of life (HrQoL) data was 93.8%. Overall compliance for all follow up was 94.6% for clinical data and 82.0% for HrQoL data. The Bang Blinding Index was 0.21 (95% Cl 0.14 – 0.27) in the laparoscopic arm and 0.53 (95% Cl 0.48 – 0.59) in the open arm which means there was a failure to adequately blind patients to treatment allocation in both groups. Patients preferred to be told of their treatment allocation in the immediate post-operative period. The majority of the trial processes were acceptable to patients and healthcare professionals. The follow up schedule was felt to be intensive due to the number of clinical visits required.

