9.4.2. RANDOMISATION PROCESS

Following confirmation of written informed consent and eligibility, patients will be randomised into the trial by an authorised member of staff at the trial site. Participant-completed baseline questionnaires (SF-12[®], EQ-5D-5L[™] and a Health Economics Questionnaire, see section 11.5) should be completed after consent has been obtained and prior to randomisation, however, where this is not possible these must be completed before the participant is informed of their randomised treatment allocation.

Randomisation will be performed centrally using the CTRU automated 24-hour randomisation system which can be accessed via the web or telephone. User ID codes and personal identification numbers (PINs), provided by the CTRU, will be required to access the randomisation system.

The following information will be required at randomisation:

- Patient details, including initials, date of birth, height and weight
- Name and code of the research site
- Name of the person making the randomisation
- Confirmation of eligibility
- Confirmation of written informed consent
- Minimisation factors (see section 9.4.3)

The randomisation system will allocate participants a unique 5 digit trial number and inform of the randomised operation for that participant (laparoscopic or open surgery).

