11.2 PRE-TREATMENT DATA COLLECTION

Participants must be screened, assessed for eligibility and have provided written informed consent before they can then be randomised (Section 9.4)

Data will be entered onto pre-operative eCRFs on the LaCeS2 database (Eligibility Checklist, Baseline and Randomisation Forms) and will include (but will not be limited to):

- Personal details and demographics including height, weight and sex
- Date of diagnosis
- Diagnosis at baseline
- Nature of intended surgical procedure
- Confirmation of eligibility
- Confirmation of written informed consent
- Minimisation factors (see section 9.4.3)
- Concomitant diseases/co-morbidities
- Details of previous abdominal operations

Following written informed consent, and wherever possible prior to randomisation (where this is not possible this must be prior to the participant being made aware of their randomised treatment), participants will also be asked to complete the baseline participant-completed questionnaires:

- SF-12[®]
- EQ-5D-5L[™]
- Health Resource Use

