11.5 PARTICIPANT-COMPLETED QUESTIONNAIRES

Participants will complete a number of health related quality of life questionnaires at various time points throughout their participation in the trial (see Table 1). The following questionnaires will be included in each questionnaire pack, unless otherwise specified:

- Gastrointestinal Quality of Life Index (GIQLI): Disease-specific HrQoL will be measured using the GIQLI. The GIQLI is composed of 36 items with 5 answer categories for each item (0-4). The GIQLI has been validated for use in patients with all gastrointestinal disease including colorectal disease requiring operative intervention [13, 14]. The GIQLI questionnaire will be included in the follow-up questionnaire packs only (i.e. at 30 days, 90 days, 6 months, 9 months and 12 months post-operation).
- **EQ-5D-5L**[™]: a well-validated questionnaire used to assess generic Quality of Life [15], it provides a simple descriptive profile and a single index value for health status.
- SF-12[®]: Generic HrQoL will be measured using the SF-12[®] questionnaire. SF-12[®] is a 12-item subset of the SF-36v2[®] that measures the same eight domains of health. The SF-12[®] is a well validated HrQoL tool for use in the acute setting with a short recall period of 1 week [16-18].
- Health Resource Use: is composed of questions related to contact with primary, community and social care services.

All participants will complete the health related quality of life questionnaire packs at baseline⁵, 30 days, 90 days, 6 months, 9 months and 12 months post-operatively.

The baseline quality of life questionnaire pack will be completed by participants on paper at the participating local research site, either in A&E, surgical assessment units, surgical wards or in clinic. Participants will be asked to seal their completed baseline questionnaire pack in a pre-supplied envelope prior to giving it to the local research staff, who will then send the sealed envelope to the CTRU for entry into the trial database.

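### The SF-12 model in Section 14.4 names no baseline score, although SF-12 is collected before the participant knows the allocation, so the key secondary analysis as written gives up precision

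*Protocol*

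**What the plan says.** Quality of life (SF-12 and GIQLI) is the key secondary outcome (Protocol Sections 3, 6.2 and 13.2). Section 14.4 sets out one linear model for all continuous secondary outcomes. They "will be analysed using multi-level linear models, adjusted for all minimisation factors", with random effects for the treating surgeon, and the models for SF-12 and GIQLI "will include an additional level to account for repeated measures". No baseline score is named.

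The minimisation factors in Section 9.4.3 are surgeon, age, BMI, ASA status, nature of pathology and intended procedure. None is a quality-of-life measure.

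Baseline is not described as a modelled response either. Section 13.2 gives only follow-up occasions: "All patient reported outcomes are collected during the 30 days, 3, 6, 9 & 12 months post-surgery".

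SF-12 is collected at baseline all the same. Under Section 11.2, "participants will also be asked to complete the baseline participant-completed questionnaires", and SF-12 is in that pack. Section 9.4.2 says that these questionnaires "should be completed after consent has been obtained and prior to randomisation"; failing that, they must be completed before the participant is told the allocation. GIQLI differs: "The GIQLI questionnaire will be included in the follow-up questionnaire packs only" (Section 11.5). In the feasibility trial, baseline compliance for "health related quality of life (HrQoL) data was 93.8" per cent (Section 5.1.1).

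**The concern.** A baseline value of the outcome, recorded before the participant knows the allocation, is a valid covariate even in an unblinded trial, and it is often among the stronger predictors of the follow-up score. The stated SF-12 model has that value available and does not use it. Two things follow. The confidence interval is wider than it need be. And if the arms happen to differ in baseline quality of life, part of that difference carries through to the estimate in the trial actually run.

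Section 14.6 says that secondary outcomes are not powered, so nothing in the design secures the precision of the quality-of-life comparison. The same protocol does provide for baseline adjustment elsewhere: the trial analysis in Section 15 adjusts for imbalance in baseline cost and utility where needed. The clinical analysis of quality of life has no matching provision.

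**Working it through.** **The plan's own figure.** For 45% against 30%, two-sided 5% and 90% power, the uncorrected size is [1.960 × √(2 × 0.375 × 0.625) + 1.282 × √(0.45 × 0.55 + 0.30 × 0.70)]² / 0.15² = 217 per arm. The continuity correction raises this to 230 per arm, or 460 in total, and 460 / 0.90 = 511.1, rounded up to 512. The stated 512 reproduces and does not depend on the SF-12 model. It supplies the number per arm used below.

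**Inputs.**
- 256 per arm (Section 9.1).
- 10% drop-out (Section 14.6), so 256 × 0.90 ≈ 230 analysed per arm. As an alternative, the 82.0% follow-up quality-of-life compliance of the feasibility trial (Section 5.1.1) gives 256 × 0.82 ≈ 210.
- ρ, the partial correlation of baseline with follow-up SF-12 given the minimisation factors. The documents do not give it; 0.2 to 0.6 is an assumption.

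**Formulae, single visit, in SD units after the minimisation factors, ignoring surgeon clustering.** Without the baseline score, SE = √(2/n). With it, SE = √(2/n) × √(1 − ρ²). The half-width of the 95% interval is 1.96 × SE. The equivalent number analysed is 2n / (1 − ρ²).

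With n = 230.4, SE = 0.0932 and the half-width is 0.183 SD on 461 patients. Adding the baseline score gives:

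| ρ (assumed) | Variance reduction | Half-width (SD) | Interval narrower by | Equivalent number analysed |
|---|---|---|---|---|
| 0.2 | 4% | 0.179 | 2% | 480 |
| 0.4 | 16% | 0.167 | 8% | 549 |
| 0.5 | 25% | 0.158 | 13% | 614 |
| 0.6 | 36% | 0.146 | 20% | 720 |

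At 82% compliance the half-width is 0.191 SD without the baseline score, 0.187 at ρ = 0.2 and 0.153 at ρ = 0.6. The percentage gains are the same.

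**Average over the five visits.** With equal correlation r between follow-up visits, the variance of a patient's mean is (1 + 4r)/5, and the proportional variance reduction is ρ² divided by that figure. For r = 0.5 (assumed) the divisor is 0.6. Then ρ = 0.2 gives 0.04/0.6 = 7% less variance (interval 3% narrower), and ρ = 0.4 gives 0.16/0.6 = 27% (interval 14% narrower). The single-visit figures therefore do not overstate the gain for an averaged effect.

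**Chance imbalance.** The baseline difference between arms has a 95% range of ±1.96 × 0.0932 = ±0.18 SD. Left unadjusted, it moves the estimate by ρ times the difference: up to about ±0.04 SD at ρ = 0.2, ±0.07 SD at 0.4 and ±0.11 SD at 0.6.

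**Missing baselines.** Feasibility compliance of 93.8% implies that 6.2% lack a baseline score. Dropping those patients would multiply the variance by about 1/0.938 = 1.066. At ρ = 0.2 the net factor is 0.96 × 1.066 = 1.023, a small loss. The sign changes at ρ² = 0.062, that is ρ ≈ 0.25. The handling rule therefore belongs with the covariate.

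**The case against.** The strongest reply is that this belongs to the SAP. Section 14.1 says that all analyses will be predefined there. Section 14.4 is one generic paragraph that also serves the complication index, gastrointestinal recovery and length of stay, none of which has a baseline score. It leaves out time effects and covariance structure too, so its silence on baseline SF-12 is weak evidence of a decision. This stands in part. A reader might infer that the protocol confines the model to the minimisation factors. It does not: nothing excludes further covariates, and an SAP could add the baseline score without contradicting the protocol. But 14.4 does state a covariate set, whereas Section 14.5 openly hands its detail to the SAP, and the stated set omits a score that is already collected.

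Four further objections stand in full:
- A reader might infer that the unadjusted estimate is biased. It is not; over repeated randomisations it is unbiased. The loss is in precision and in accuracy given the imbalance that occurs.
- A reader might infer that baseline SF-12 goes to waste. Section 15 plans a supplementary SF-6D analysis derived from SF-12, with utility data captured at baseline, so it has another use.
- The size rests on an assumed partial correlation. SF-12 has a one-week recall (Section 11.5) and is completed in acute illness, and age and ASA are already in the model. The gain may be near 2%.
- No document relates SF-12 to GIQLI, so the case for baseline SF-12 in the GIQLI model has no figure behind it.

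**Conclusion.** The point holds for SF-12 PCS and MCS. The model as stated names no baseline score, although one is collected before the participant knows the allocation, and including it is a better analysis at no data cost. With an assumed partial correlation of 0.2 to 0.6, the single-visit confidence interval would be about 2% to 20% narrower, and the shift from a chance imbalance at the edge of its 95% range would be about 0.04 to 0.11 SD. The lower figures are plausible here.

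This is a worthwhile improvement to a key secondary analysis. It does not threaten validity, and the documents support no conclusion about the primary analysis or the sample size, which stay as they are.

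**What to change.** In Section 14.4, add that the SF-12 PCS and MCS models also include the corresponding baseline score, either as a covariate with a baseline-by-visit interaction or by modelling baseline jointly with the follow-up scores. Make this unconditional, so that it does not depend on the imbalance observed.

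State with it that a missing baseline score used as a covariate is handled by mean imputation (the mean taken over both arms together) or by a missing indicator, so that no randomised patient is dropped.

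Baseline PCS and MCS in the GIQLI model may be considered, as an option only.

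The cost is a sentence or two in the protocol, carried into the SAP before analysis. No new data, visit or questionnaire is needed. If the correlation proves close to zero, the expected loss from the extra covariate is negligible.
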